5.2 Secondary endpoints

Variables for the evaluation of beta cell insulin secretion capacity and metabolic control.

Stimulation tests: glucagon-stimulated C-peptide test (GSCT) [36] and mixed meal tolerance test (MMTT) [37].

- 1) Insulin secretion measured by glucagon- and MMTT stimulated C-peptide at baseline, and at 5 and 12 months after the first injection
- 2) Change in HbA1c from baseline to 5 and 12 months after the first injection
- 3) Change in fasting glucose from baseline to 5 and 12 months after the first injection.
- 4) Change in Fasting C-peptide between baseline and 5 and 12 months after the first injection

- 5) Change in maximum C-peptide during MMTT between baseline and 5 and 12 months after the first injection.

Variables for the evaluation of immunological response at 5 and 12 months vs. baseline:

- 6) Measurement of serum concentration of GAD65-specific IgG1, IgG2, IgG3 and IgG4 antibodies for all included patients
- 7) Measurement of supernatant concentrations of IL-1, IL-2, IL-5, IL-13, IL-10, IL-17, IFN- γ and TNF secreted during cultivation of PBMCs isolated from all included patients
- 8) Characterization of PBMCs with FACS using CD3, CD4, CD8, CD45RA, CCR7, CD25, CD127, FOXp3 at baseline
- 9) Analyze the proliferation of PBMCs isolated from all included patients during cultivation with vehicle, GAD65 and control antibody.
- 10) Other relevant variables.

5.3 Trial description

The proposed study is an open label Phase IIa feasibility trial. It is a pilot study that does not include a placebo arm. The time course of beta cell function in the trial will be compared to that in our recent trial, BALAD (described in 3.3.1), as a historical control. A positive outcome (i.e. no safety concerns, a robust immunological response and a favorable time course of beta cell function compared to BALAD) will pave the way for a placebo-controlled phase III study.

5.4 Time line and main study events

The project is expected to take 2 years. Given that LADA patients constitute 10% of the total diabetes population, our expectation is that the study could be fully recruited within 1 year. Each patient will then be followed for 12 months. Study close out, data cleaning and analysis, compilation of final report, etc. will take place during the final 6 months of the project. The schedule of the main study events is given in Table 1. The end of the trial is defined as the last visit of the last patient included in the trial and the time point where all data have been collected.

Table 1: Schedule of main events for the trial

Event	V1 Screening	V2		V3 Baseline		V4 ^a M1	V5 ^a M2		V6 M5		V7 M12	
		-44 to -60	-31	-30	1	2 (+2)	30 (±5)		150 (±14)	151 (+2)	360 (±14)	361 (+2)
DAY	-44 to -60	-31	-30	1	2 (+2)	30 (±5)	60 (±5)	90	150 (±14)	151 (+2)	360 (±14)	361 (+2)
Informed consent	X	X										
Demographics	X											
GAD-alum (4 µg) a, b, c,					X	X	X					
Vitamin D ^d start /end			Start					Stop				
Neurological assessment	X			X		X	X		X		X	
Concomitant medication	X			X		X	X		X		X	
Vital signs (BP)	X			X		X	X		X		X	
Injection site inspection; investigator/study nurse ^e					X	X	X					
AEs				X		X	X		X		X	
Glucagon test ^{c,f}			X		X					X		X
MMTT ^f		X		X					X		X	
Blood and urine sampling for safety, genetics, vitamin D levels and immunology:												
Hematology	X			X		X	X		X		X	
Clinical Chemistry	X			X		X	X		X		X	
GAD65A titer^g	X			X		X	X		X		X	
HLA characterization				X								
Vitamin D level	X	X		X		X	X		X		X	
Other immunological parameters^h		X		X		X	X		X		X	
Creatinine	X			X		X	X		X		X	
Blood sampling for diabetes status:												
Fasting C-peptide	X	X	X	X	X	X	X		X	X	X	X
Fasting glucose	X	X	X	X	X	X	X		X	X	X	X
Glucagon stimulated C- peptide and glucose			X		X					X		X
MMTT stimulated C-peptide		X		X					X		X	
MMTT stimulated glucose		X		X					X		X	
HbA1c	X	X		X		X	X		X		X	

[Abbreviations for Table 1: V= visit; M=month; GAD= Glutamic Acid Decarboxylase; BP=Blood Pressure; AEs=Adverse Events; MMTT=Mixed Meal Tolerance Test; GAD65A=Glutamic Acid Decarboxylase Antibodies; HLA=Human Leukocyte Antigen; HbA1c=Hemoglobin A1c]

- a. Study drug administration: For visit 4 and 5 the visit date must be set in accordance with visit 3 and 4, respectively, so that the first, second and third doses will be 30 days apart (\pm 5days).
- b. The GAD-alum injection directly into the inguinal lymph node is to be done by an appropriately qualified radiologist at the X-ray department at the study site by help of ultrasound technique.
- c. On day two at visit 2, the glucagon test needs to be done before the injection of GAD-alum.
- d. Supplementation with vitamin D starts at day -30, after the glucagon test has been performed, if the vitamin D serum levels are below 100 nmol/L (40 ng/ml) at screening. If the patient has vitamin D serum levels above 100 nmol/L (40 ng/ml) at screening, no Vitamin D supplementation will be given for that patient.
- e. The investigator/study nurse will inspect the injection site before and after the injection is given and record any injection site reactions in the Case Report Form (CRF).
- f. The MMTT and the Glucagon test must be carried out on separate days, as each test has to be performed in the fasting state.
- g. Antibodies against IA-2 (islet cell antigen 2), ZnT8 (Zink transporter 8) and insulin will be measured at Baseline and at Visit 7.
- h. Antibodies against SARS-CoV-2 will be measured at Visit 6 and Visit 7.

6. SELECTION AND WITHDRAWAL OF SUBJECTS

6.1 Informed consent

Potential study patients will receive both written and oral information about the study procedures, potential risks, and benefits. Before any study specific procedures may be performed, the patients must sign an informed consent form.

6.2 Medications other than the study drug

Antidiabetic medication in the form of metformin is acceptable before and during the trial.

Study participants must be insulin independent at baseline, but if the need for insulin treatment develops during the trial, such treatment will be given. The need for insulin treatment will be based on clinical judgement after considering the following parameters:

- Increased levels of HbA1c, i.e. two measurements, performed 1 month apart, showing an increase of 22 mmol/mol vs. baseline
- Fasting blood glucose >10 mmol/L in at least 3 occasions during a single week
- Weight loss >2 kg vs. baseline.

6.3 Inclusion and exclusion criteria

Inclusion criteria:

1. Signed informed consent by the patient.
2. Diagnosis of LADA and diabetes debut within the last 18 months before inclusion. LADA should be defined by the criteria of age \geq 30 years at the onset of diabetes, anti-GAD positivity and no clinical need for permanent treatment of insulin during the first 3 months after the diagnosis of diabetes.
3. Male or female between 30-70 years of age

4. Fasting C-peptid levels ≥ 0.3 nmol/l
5. High GADA titers (>190 U/ml)
6. Patients must be insulin independent at baseline by clinical judgement and C-peptide criteria
7. Antidiabetic medication in the form of metformin is acceptable for inclusion as well as medications not mentioned under exclusion criteria
8. Females must agree to avoid pregnancy and have a negative urine pregnancy test.
Patients of childbearing potential must agree to use adequate contraception, until one (1) year after the last administration of GAD-alum. Adequate contraception is as follows:

For females of childbearing potential:

- a. oral (except low-dose gestagen (lynestrenol and norestisteron)), injectable, or implanted hormonal contraceptives
- b. combined (estrogen and progestogen containing)
- c. oral, intravaginal or transdermal progesterone hormonal contraception associated with inhibition of ovulation
- d. intrauterine device
- e. intrauterine hormone-releasing system (for example, progestin-releasing coil)
- f. bilateral tubal occlusion
- g. vasectomized male (with appropriate post vasectomy documentation of the absence of sperm in the ejaculate)
- h. male partner using condom
- i. abstinence from heterosexual intercourse

For males of childbearing potential:

- a. condom (male)
- b. abstinence from heterosexual intercourse

Exclusion criteria:

1. Current or previous treatment with immunosuppressant therapy (topical or inhaled steroids are accepted)
2. Continuous treatment with anti-inflammatory drug (sporadic treatment e.g. because of headache or in connection with fever a few days will be accepted)
3. Systemic treatment with glucocorticoids
4. Treatment with any vaccine, including influenza vaccine, within 1 month prior to planned first study drug dose or planned treatment with any vaccine up to 1 month after the last injection with study drug
5. Antidiabetic medication (metformin excepted)
6. Significantly abnormal hematology results at screening (i.e. anemia with hemoglobin < 12 g/L).

7. A history of epilepsy, head trauma or cerebrovascular accident, or clinical features of continuous motor unit activity in proximal muscles
8. Clinically significant history of acute reaction to vaccines in the past.
9. Renal disease (as defined by serum creatinine >150 µmol/l)
10. Serious cardiovascular events (myocardial infarction, stroke) within the last year preceding recruitment.
11. Participation in other clinical trials with a new chemical entity within the previous 3 months
12. A history of alcohol or drug abuse
13. Known HIV or hepatitis
14. Presence of associated serious disease or condition, including active skin infections that preclude intralymphatic injection, which in the opinion of the investigator makes the patient non-eligible for the study
15. Other serious chronic disease as judged by investigator.
16. Females who are lactating, are pregnant or intend to become pregnant.
17. Inability or unwillingness to comply with the provisions of this protocol
18. Deemed by the investigator not being able to follow instructions and/or follow the study protocol
19. Treatment with any other supplementation of vitamin D, marketed or not, or unwilling to abstain from such medication during the 120 days daily intake of Divisun (non-investigational medicinal product)

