3.6 Study population

Study participants are to be men and women between 30-70 years of age, that have been diagnosed with LADA within the last 18 months, i.e. being GADA positive and insulin independent at baseline. Based on the findings in our recent trial, BALAD (see 3.3.1), we will include only those with high GADA titers (>190 U/ml).

Altogether approximately 15 LADA patients will be recruited from one clinic in Norway (St Olavs Hospital, Trondheim) and one in Sweden (Karolinska University Hospital, Stockholm). Recruitment will be through advertisement in journals for diabetic patients and information through other media outlets as well as by referrals from physicians treating patients for

diabetes. Given that LADA patients constitute 10% of the total diabetes population we foresee that the study will be fully recruited within 1 year.

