5. TRIAL DESIGN

5.1 Primary endpoint

Variables for the evaluation of safety and feasibility:

- 1) Injection site reactions, skin reactions 1 hour post injection vs. before injection.
- 2) Occurrence of AEs, continuously registered and status summarized at 5 and 12 months after the first injection.
- 3) Laboratory measurements (hematology and clinical chemistry), status summarized at 5 and 12 months after the first injection vs. baseline.
- 4) Physical examinations, including neurological assessments, status summarized at 5 and 12 months after the first injection vs. baseline.
- 5) GAD65A titer in serum, levels at 5 and 12 months after the first injection vs. baseline.
- 6) Vital signs (blood pressure), status summarized at 5 and 12 months after the first injection vs. baseline.

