9. SAFETY AND ADVERSE EFFECTS

9.1 Safety parameters

See also Section 5.1, Primary endpoint, and Table 1.

The safety assessments include occurrence of adverse events (AEs), laboratory measurements, physical examinations including neurological assessments. Adverse events will be recorded by the physician at every visit throughout the study.

Blood tests for safety:

- Chemistry: Creatinine, Calcium, Liver function tests (alanine aminotransferase (ALT), aspartate aminotransferase (AST), alkaline phosphatase, bilirubin)
- Haematology (MHC, MCV, MCHC, Haemoglobin, Platelets, Leukocytes)

Urinalysis for safety:

- Urine pregnancy test as appropriate
- Microalbuminuria
- Creatinine

Other Variables which will be evaluated:

- Inflammatory markers, especially TNF-alfa, IL-1 beta, IL-2, IL-17
- Th2-deviation of cell-mediated immune response seen e.g. as increased ratio of IL-5,10, 13 in comparison with IFN-gamma, TNF-alfa, IL-1 beta and IL-17, and increase of T-regulatory cells
- C-peptide (90 minute value and AUC mean 0-120 min) during an MMTT
- Fasting C-peptide
- HbA1c
- D-vitamin
- Antibodies against SARS-CoV-2 (at Visit 6 and 7)

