10.2 Estimation of sample size

The proposed study is an open-label pilot phase IIa trial and will include approximately 15 patients. No formal power analyses are performed for this pilot study.

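### Exclusion 6 prints the hemoglobin limit as 12 g/L (1.2 g/dL), which cannot screen out anemia, and the protocol gives no other limit to fall back on

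*Combined protocol and SAP*

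**What the plan says.** Section 6.3, exclusion 6, removes patients with "Significantly abnormal hematology results at screening (i.e. anemia with hemoglobin < 12 g/L". The wording makes the number the definition of a significantly abnormal result, not an example of one.

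The protocol touches on the subject in three other places, none with a limit:

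- Section 9.1 names the safety variables: "Haematology (MHC, MCV, MCHC, Haemoglobin, Platelets, Leukocytes". No units or ranges are attached.
- Section 5.1, item 3, makes hematology part of the primary safety evaluation: "Laboratory measurements (hematology and clinical chemistry), status summarized at 5 and 12 months after the first injection vs. baseline".
- Table 1 schedules hematology at visits 1, 3, 4, 5, 6 and 7.

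Two further exclusions leave room for judgement. Number 14 covers serious disease or conditions "which in the opinion of the investigator makes the patient non-eligible for the study", and number 15 reads "Other serious chronic disease as judged by investigator".

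For contrast, exclusion 9 gives its laboratory limit in a form that can be applied: "Renal disease (as defined by serum creatinine >150 µmol/l".

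**The concern.** The purpose of exclusion 6 is plain: to keep anemic patients out. The printed value does not do that. A hemoglobin of 1.2 g/dL is far below anything seen in a person who walks into a clinic, so the criterion taken at its word excludes nobody on hemoglobin.

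What is at stake is eligibility and its consistency. Section 3.6 states: "Altogether approximately 15 LADA patients will be recruited from one clinic in Norway", with a second clinic in Sweden. Each site has to ignore the line, correct it silently, or turn to the judgement-based exclusions 14 and 15. A site that applies a sensible limit departs from the written protocol, while a site that admits an anemic patient complies with it. Two checks inherit the difficulty. The monitor (section 11) has no usable value against which to verify this criterion. And the per-protocol population in section 6.4b, which requires freedom from major violations, cannot be settled for an anemic entrant from the printed limit.

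**Working it through.** **Inputs from the protocol**

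- Printed limit: hemoglobin below 12 g/L (section 6.3, exclusion 6).
- Planned sample: about 15 patients at two sites (sections 3.6 and 10.2).
- Hematology variables: six (section 9.1).

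**Input assumed, not in the protocol**

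- Hemoglobin of a deeply anemic patient who can still attend as an outpatient: 40 to 70 g/L.

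**Step 1: convert the printed limit.** 1 dL is 0.1 L, so g/L ÷ 10 = g/dL, and 12 ÷ 10 = 1.2 g/dL. The same digits read in g/dL would be 12 × 10 = 120 g/L, so the two readings differ by a factor of 120 ÷ 12 = 10. This shows how much hangs on the unit; it does not show what the sponsor intended.

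**Step 2: set the limit against a patient it ought to catch.**

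| Assumed hemoglobin | Divided by printed limit | Excluded as printed? |
|---|---|---|
| 40 g/L | 40 ÷ 12 = 3.3 | no |
| 70 g/L | 70 ÷ 12 = 5.8 | no |

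The conclusion does not hang on the exact range. Any value of 12 g/L or more passes.

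**Step 3: look for a second value that would resolve it.**

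| Place | Content | Limit or unit? |
|---|---|---|
| 6.3, exclusion 6 | hemoglobin limit | yes, not usable as printed |
| 9.1 | hemoglobin as one of six variables | none |
| 5.1, item 3 | hematology against baseline | none |
| Table 1 | hematology at six visits | none |

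There is no reference range and no statement of reporting units. HbA1c is a different measurement and does not help. The other five variables in section 9.1 have no entry limit either. That is not a fault in itself, but it means the numeric part of exclusion 6 rests on this one figure.

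**Step 4: scale.** One patient treated differently by the two sites is 1 ÷ 15 = 6.7% of the planned sample. This is the weight of a single patient, not an estimate of how many are affected; that number cannot be derived from the documents.

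**The case against.** The strongest reply is that this is an evident slip which any clinician would read correctly, and that nothing depends on it. Part of that stands. If one explanation is much the most likely, both sites may make the same correction, and nothing in the documents shows that they would diverge. The opening words of exclusion 6 still direct the investigator to the screening blood count. Exclusions 14 and 15 allow an unfit patient to be refused. Table 1 appears to place a further hematology sample on day 1, ahead of the first injection on day 2, although the protocol does not require that result to be seen before dosing. Hemoglobin is then followed through visit 7, so safety monitoring is not lost. The study is a single-arm, descriptive pilot for which "No formal power analyses are performed for this pilot study", so no calculation is disturbed.

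It can also be said that a character was lost when the PDF was converted to text. That cannot be excluded entirely, but the sentence shows no gap and the neighboring creatinine limit is intact. A look at the source file settles it.

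None of this makes the printed line right. The protocol chose to define the criterion by a number, and an eligibility limit should not have to be guessed, even if the guess is likely to be a common one.

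**Conclusion.** The concern holds. The only hemoglobin limit in the protocol, 12 g/L or 1.2 g/dL, cannot serve the purpose stated in the same sentence, and no other section supplies a value. Either the number or the unit is wrong; the documents do not show which.

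The conversion is exact. The claim that the criterion excludes nobody rests on one assumption from outside the documents, that patients attending screening have a hemoglobin well above 12 g/L. The 40 to 70 g/L range illustrates it generously.

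The consequence is limited to eligibility and to consistency between the two sites. Each discordant admission would be about 6.7% of the sample, and there may be none. Sample size, analysis and conclusions are unaffected. It should be fixed because it is a wrong threshold in a working eligibility criterion and is cheap to correct, not because it endangers the trial.

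**What to change.** 1. The sponsor checks exclusion 6 against the source document and confirms the intended limit.
2. The criterion is reprinted with number and unit in agreement, in the unit that both site laboratories report. The choice of limit belongs to the sponsor; none is suggested here.
3. Any eligibility check on hemoglobin in the eCRF is aligned with the corrected text.
4. If screening has begun (section 1.6 plans recruitment from Q1 2020), the screening hemoglobin of every patient already screened is compared with the corrected limit, and any discrepancy is documented.

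The cost is a one-line correction, at most a small change to the eCRF, and a review of a small number of values. The possible downside is some additional screen failures, or none if the sites already apply a sensible limit.

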6.4 Withdrawal criteria

a) When and how to withdraw subjects from the trial

In accordance with the Declaration of Helsinki, the investigator must explain to the patient that they have the right to withdraw from the study at any time, and that this will in no way prejudice their future treatment. The reason for any kind of withdrawal must be recorded in the CRF.

There will be two main categories for withdrawals from the study:

Complete withdrawal (i.e. stopping investigational product(s) and also continued efficacy and safety evaluations). In order to achieve as complete as possible 12 month follow-up, whenever feasible, patients that are considered for complete withdrawal should be asked if they could consider to return for a 12-month visit. Attempts should be made to contact patients lost to follow-up with respect to this.

Standard reasons for withdrawing from further participation in the study and from the follow-up visits may be:

- Patient's decision (withdrawal of consent to participate)
- Patient lost to follow-up

Withdrawals from investigational product(s) (i.e. stopping one or several investigational products, but continuing follow-up visits, including efficacy and safety evaluations)

Standard reasons from withdrawing from taking further investigational product, but continuing follow-up visits and safety evaluations may be:

- Unacceptable AEs
- Patient request
- Investigator's discretion
- Patient lost to follow-up/non-attendance
- Intercurrent illness
- The patient becomes pregnant

Criteria for terminating the investigational product treatment/trial treatment:

Rapid increase in HbA1c or decline in C-peptide levels vs. historical controls. Evidence for induction of stiff person syndrome (SPS) or any adverse neurological or behavioural effects.

GAD-alum should not be given to the patient if the patient after inclusion in the study develops/experiences:

- Brain damage, epilepsy, head trauma, neurological disease
- Any active, serious hormonal disease other than LADA
- Other severe autoimmune disease (except celiac disease which is accepted for inclusion)
- Immune-suppressive treatment
- Cancer, cancer treatment
- Any vaccination
- Drug/alcohol abuse
- Becomes pregnant or is no longer willing to use safe contraceptives during the study

Vitamin D supplementation should not be continued if the patient after inclusion in the study develops/experiences:

- Symptoms of hypercalcemia such as tiredness, euphoria, drowsiness, nausea, weight loss, thirst, polyuria, nefrocalcinosi, renal failure
- Arrhythmia
- Pancreatitis

b) The type and timing of the data to be collected for withdrawn subjects

Intention-to-treat population

Patients will be included in the primary intention to treat population for analysis of efficacy if they receive at least 1 dose of GAD-alum and are assessed at a later visit.

Per protocol population

The subjects must have followed the protocol without any major violations. Any examinations/tests missed will be substituted with the last observation carried forward, but examinations/tests from not more than 1 visit may be lost.

Total population

Any patient who withdraw from the study will be included in the safety analysis (adverse events and safety parameters). Data for all patients will be listed, and a list of withdrawn patients, with all reasons for withdrawal, will be given.

c) Follow up of subjects withdrawn from investigational product treatment/trial treatment.

Withdrawals due to non-attendance must be followed up by the investigator to obtain the reason for non-attendance. Withdrawals due to any illness or AEs must be fully documented in the CRF.

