In the recently published BALAD trial [8] we randomized LADA patients to add-on treatments with either insulin (primarily nighttime NPH insulin, i.e. intermediate acting insulin) or a DPP-4 inhibitor, sitagliptin (trade name Januvia), 100 mg daily. Here we show that early insulin treatment does not provide any added benefit when compared to sitagliptin. Further, following patient stratification at inclusion into low and high GADA titer groups, (cutoff 190 U/ml) results show a clear deterioration of stimulated C-peptide parameters in participants in those of the high GADA category. The decline in stimulated C-peptide amounted to a median of 38% compared with results obtained at the time of randomization.

Taken together these findings demonstrate the inability of standard therapeutic modalities to modify the impact of autoimmunity in LADA. We conclude that a new therapy is needed that directly counters autoimmunity in LADA patients displaying high titers of GADA.

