Results with intranodal injections of GAD-alum are available from a 15-month proof-of-concept phase I/II clinical trial DIAGNODE-1 (NCT02352974) [16]. DIAGNODE-1, is an open-label trial of intralymphatic rhGAD therapy together with vitamin D supplementation for 12 patients aged 12 to 24 with residual beta cell activity diagnosed with type 1 diabetes within six months of inclusion. This study employs three low doses (4 µg each) of GAD-alum that are administered directly into an inguinal lymph node using ultrasound guided injections. The disease progression appears very positive in terms of partial remission, levels of stimulated C-peptide, HbA1c and insulin dose. Using the compound variable insulin dose-adjusted HbA1c (IDAAC) as a marker, 11 of 12 patients attained partial remission after 15 months (IDAAC \leq 9) ([name], unpublished data). In comparison, less than 20% of children and adolescents with new-onset T1D in a cohort (N=3657) followed over six years were in partial remission 18 months after diagnosis [17].

After 15 months, stimulated C-peptide area under the curve (AUC) decreased by only 19% in treated patients. In contrast, a matched untreated control population of 27 patients (historical controls) selected from the placebo arm of a different Diamyd trial in the same patient age-range showed an average decrease of between 40% and 50% [18]. The positive effects on beta cell function reported in the DIAGNODE-1 trial are accompanied by a reduction in HbA1c by 18% (compared to a 15% increase in controls), and average insulin dose increase of only 6% (compared to more than a 50% increase in controls) ([name], unpublished data).

Immunological response to intralymphatic administration was characterized by a relative reduction of IgG1, with a shift towards IgG2, IgG3 and IgG4 subclasses after 3 intra-lymphatic injections of GAD-alum ([name], unpublished data). This finding is significant as both IgG2 and IgG4 have low respectively no ability to bind complement and an IgG4 response is associated with long-term immunotherapy response in the allergy field [15]. Further, while IgG1 is the dominant GAD antibody subclass in type 1 diabetes, IgG4 is more common in

LADA, suggesting that subclass distribution is an important aspect of the underlying disease mechanism [19].

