8.2 Methods for the recording of effect parameters

The patient must attend all study visits in the morning following an overnight fast (>10 hours, water allowed). Each visit should be completed as scheduled (see Table 1). However, for patients with evidence of an infection, the visit should be postponed until the patient has recovered.

8.2.1 *Endogenous insulin production: Visit 2, 3, 6 and 7*

The MMTT [37] and the GSCT [36] must be performed according to the instructions in the specific laboratory manuals. The tests must be carried out on separate days, as each test has to be performed in the fasting state. Also, if the patient develops need for insulin treatment during the study period, the patient must not take short acting/direct acting insulin within 6 hours before the test. The patient is allowed to take base-insulin the day/night before, but not in the test morning and during the MMTT and the GSCT. If the patient does not fulfill the above mentioned criteria, the MMTT and GSCT should be rescheduled and the patient return to the study site within 5 days if possible.

MMTT: The patient will be given a standardized liquid nutrition mixture. Blood samples will be secured for glucose and C-peptide measurements at before and 0, 30, 60, 90 and 120 (± 5) minutes after the meal.

GSCT: The patient will receive an intravenous injection of 0.5 mg glucagon. Blood samples will be secured both before and 6 minutes after the injection for the measurements of glucagon-stimulated C-peptide and glucose.

8.2.2 *Immunological tests: Blood samples collected at all visits: Visit 2-7*

Measurements of GADA titer and some of the relevant immunological parameters will be performed at the Department of Clinical and Molecular Medicine, NTNU. Measurements of Anti-SARS-CoV-2 will be performed at Laboratoriemedisinsk klinikk, St Olavs Hospital, Trondheim, and at Karolinska Universitetslaboratoriet, Stockholm. HLA classification will be

performed at Oslo University Hospital Rikshospitalet, Department of Immunology and Transfusion medicine. Classification and analyses of T-cells and other relevant immunological tests will be performed at Linköping University Hospital.

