10.3 Missing data

See Section 6.4b.

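### The only missing-data rule is LOCF for the per-protocol set: it would understate any fall in stimulated C-peptide, and the primary ITT efficacy set has no stated rule

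*Combined protocol and SAP*

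**What the plan says.** Section 10.3 (Missing data) consists of one cross-reference: "See Section 6.4b". Section 6.4b defines three populations.

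- **Intention-to-treat:** "Patients will be included in the primary intention to treat population for analysis of efficacy if they receive at least 1 dose of GAD-alum", provided there is also an assessment at some later visit. No rule for missing values follows.
- **Per protocol:** no major violations, and "Any examinations/tests missed will be substituted with the last observation carried forward, but examinations/tests from not more than 1 visit may be lost".
- **Total population:** for safety.

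The heading of section 8.2.1 fixes the stimulation tests: "Endogenous insulin production: Visit 2, 3, 6 and 7". V2 and the tests at V3 precede the first injection, V6 is month 5 and V7 is month 12. In Table 1 the row "MMTT stimulated C-peptide" is empty at V4 and V5, as is the glucagon-test row. Fasting C-peptide, fasting glucose and HbA1c are measured at V4 and V5.

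Section 10.1 plans descriptive summaries by visit with the number of observations. It ties no analysis to the ITT or per-protocol set and does not say whether imputed values enter the tables. Section 5.3 makes "a favorable time course of beta cell function compared to BALAD" one of three conditions for a positive outcome.

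**The concern.** LOCF suits a quantity that stays put between visits. The protocol describes the opposite for this population. Of BALAD's high-GADA patients, section 3.3.1 says: "The decline in stimulated C-peptide amounted to a median of 38% compared with results obtained at the time of randomization". With only two post-dose stimulation tests, seven months apart, a carried value is either seven months old (V7 missed) or a pre-dose value (V6 missed). In a declining population both make the per-protocol decline look smaller than it is. The exact-zero problem is confined to stimulated C-peptide, because a missed V6 for the fasting measures and HbA1c is filled from V5 at month 2.

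The ITT set raises a separate question. A patient dosed once and seen again only at V4 or V5 qualifies for it without any post-dose stimulation test. The plan does not say how that patient, or any ITT patient with a missing test, is handled, so the choice could be made after the data are seen.

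Missing tests may also be related to decline. Under section 6.2 insulin may be started during the trial. Under section 8.2.1 a patient on insulin must meet extra conditions before a test, or return within a few days if possible. That is a possible route, not a demonstrated one.

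**Working it through.** The plan gives no expected decline for this trial, no dropout rate and no figure for the effect of LOCF, so there is no stated figure to reproduce. The check asks how far one carried value moves the mean of 15 (section 10.2 says approximately 15) under decline rates that the documents report for other patients.

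**Inputs**
- BALAD, high GADA: median decline 38% (section 3.3.1, no time point given). The synopsis gives the trial length as 21 months, so 21 months is inferred. The median stands in for a mean.
- Intralymphatic pilot in type 1 diabetes (section 3.3.3): "After 15 months, stimulated C-peptide area under the curve (AUC) decreased by only 19% in treated patients".
- Assumed path: constant proportional decline, D(t) = 1 − (1 − d)^(t/T), with the linear path d·t/T as a check.

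**Missed V7, month 5 carried to month 12.** Shift per patient = [D(12) − D(5)]/15.

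| Assumed decline | D(5) | D(12) | Difference | Shift, proportional | Shift, linear |
|---|---|---|---|---|---|
| 38% over 21 months | 10.8% | 23.9% | 13.1 | 0.88 | 0.84 |
| 19% over 15 months | 6.8% | 15.5% | 8.7 | 0.58 | 0.59 |
| 38% by month 12 (not stated) | 18.1% | 38.0% | 19.9 | 1.33 | 1.48 |
| No change | 0 | 0 | 0 | 0 | 0 |

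If C-peptide rises after month 5, the sign reverses.

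**Missed V6, pre-dose value carried to month 5.** Shift = D(5)/15: 10.8/15 = 0.7 points on the BALAD path, 6.8/15 = 0.5 on the slower path.

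**Several missing.** Suppose 3 of 15 miss V7 (an assumption) on the BALAD path. LOCF gives (12 × 23.9 + 3 × 10.8)/15 = 21.3% instead of 23.9%.

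**Would observed values alone be enough?** Let those 3 decline at twice the rate: 1 − 0.62^(24/21) = 42.1% at month 12 and 1 − 0.62^(10/21) = 20.4% at month 5.
- True mean: (12 × 23.9 + 3 × 42.1)/15 = 27.5%.
- LOCF: (12 × 23.9 + 3 × 20.4)/15 = 23.2%, hiding 4.3 points.
- Observed only: 23.9%, hiding 3.6 points.

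At three times the rate the order reverses (true 30.3%, LOCF 24.9%, observed only 23.9%). Observed-only summaries are therefore not a full cure.

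**Repeated-measures estimate.** Simulation with 20,000 runs per setting: n = 15, 3 without V7, maximum likelihood on log change at months 5 and 12, assumed patient-slope SD 0.01 to 0.02 per month and test SD 0.10 on the log scale. Geometric-mean decline at month 12, %:

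| Who misses V7 | True | LOCF | Observed only | Model |
|---|---|---|---|---|
| Random 3 | 23.9 | 21.4–21.5 | 23.9–24.0 | 23.9–24.0 |
| 3 largest month-5 falls | 23.9 | 21.0–22.3 | 18.9–21.2 | 23.9–24.0 |
| 3 declining twice as fast | 27.9–28.0 | 23.2–23.3 | 23.9–24.0 | 25.1–25.9 |

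**Scale against noise, same assumed SDs.** SD of a log change at month 12 = √[(12s)² + 2 × 0.10²], which is 0.185 for s = 0.01 and 0.279 for s = 0.02. Dividing by √15 and multiplying by 0.761 (= 1 − 0.239) gives a standard error of 3.6 to 5.5 points. One missed V7 (0.9) is about a sixth to a quarter of that.

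**The case against.** The strongest reply is that the size is conditional and the stakes are low. The trial tests for preservation, and section 3.3.3 reports improved beta-cell function for up to two years after a subcutaneous dose in LADA. If the treatment works, there may be little decline to hide. C-peptide is secondary and descriptive, section 10.2 disclaims power, and section 10.1 calls the BALAD comparison mainly a pointer for future research. Several provisions limit missing data: the month-12 return request (6.4a), rescheduling (8.2.1) and the required explanation of missing data (14.1). All of this stands, and it limits the severity. None of it is an analysis rule.

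It can also be said that by-visit tables with n already point to observed-case reporting for ITT. That is a fair reading, and it makes the ITT gap mostly one of missing detail, but the plan does not say so.

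A log-scale model may look like too much for 15 patients, and the simulation above generates data on the scale that the model uses, which favours it. That is why it is proposed beside the observed values rather than instead of them.

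Three stronger readings are tempting and not supported:
- A reader might infer a fixed bias of 0.6 to 1.3 points. The documents give no decline for this trial. The upper figure needs the full 38% by month 12, which is nowhere stated, and zero or a reversed sign is possible.
- A reader might infer that the BALAD contrast is tilted towards the treatment. How BALAD handled missing values is not stated, so the net effect is unknown.
- A reader might infer that LOCF governs the primary efficacy set. It is written only for the per-protocol set.

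**Conclusion.** The point holds in conditional form. The one stated imputation rule gives wrong month-5 and month-12 stimulated C-peptide values whenever function changes between visits. Under the decline that the protocol itself describes, the error makes the per-protocol loss look smaller. The central figure is about 0.9 points of the mean of 15 per missed V7, and about 0.6 at the slower rate. These figures rest on a smooth path, a median used as a mean, an inferred 21-month time point and all 15 patients being in the per-protocol set. The shift would not by itself make the treatment look protective. The absent ITT rule adds an open choice rather than a known bias. Overall this is a minor-to-moderate fix.

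**What to change.** In sections 6.4b and 10.3:

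1. Remove LOCF as the main rule for stimulated C-peptide. Keep it at most as a labelled sensitivity analysis, and name the population that each rule covers.
2. For both the ITT and per-protocol sets, summarise months 5 and 12 from tests actually done at that visit, with n.
3. List patients without a post-dose stimulation test, with reasons and any start of insulin.
4. Add a simple repeated-measures estimate on log C-peptide using all observed visits, because observed-only summaries are also biased when faster decliners are the ones missing.
5. Handle the BALAD data the same way where patient-level data allow. Otherwise state how BALAD handled missing values.

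The cost is a few sentences and one small model, with no new visits or data. The downsides are a slightly smaller n per visit and some remaining bias if missingness depends on unobserved decline. In the twice-as-fast simulation the model still fell 2.1 to 2.8 points short.
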